Diabetes and CLI: Nearly 30 million Americans suffer from diabetes – a chronic metabolic disorder characterized by inappropriate hyperglycemia and increased risk of cardiovascular disease [13]. Diabetes is associated with altered serum lipidomics, endothelial cell dysfunction, and impaired arterial collateral formation [13]. These pathophysiologies make diabetic patients particularly prone to developing a distinct pattern of diffuse and recalcitrant peripheral arterial disease that leads to advanced CLI. Chronic inadequate supply of oxygen and nutrients to the extremity of these patients can lead to end-stage complications like non-healing wounds, infection, and gangrene [14]. Despite recent advances in the treatment and management of diabetic patients, CLI remains highly prevalent in this patient population, and results in high rates of major extremity amputations. Even when major extremity amputations are performed, healing at the surgical site in patients with diabetes is impaired due to poor blood flow at the arterial cul-de-sac in the newly created amputation stump [15]. At the present time, there are no widely accepted treatment strategies to augment tissue perfusion in ischemic peripheral tissue

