Aside from smoking cessation and physical exercise, there are currently no known effective medical treatments for patients with advanced non-surgically correctable CLI [13, 21]. In addition, the prevalence of amputations resulting from CLI among diabetic patients is disturbingly high [2]. Based on our recent preclinical studies, we are proposing a pilot clinical trial to further explore the potential therapeutic benefits of NAC in healing extremity amputation stumps in the setting of CLI, plus or minus diabetes. These studies are highly innovative in that they: i) explore a compelling new modality of therapy in a highly vulnerable, but frequently under-represented clinical trial patient population, ii) explore a completely novel and not previously reported NAC mechanism of action on phospholipid synthesis and expression, and iii) represent the potential use of a low-cost, generic pharmacological agent, which would otherwise not be pursued by drug pharmaceutical manufacturers due to low-profit margins. In short, this proposal may establish a conceptual infrastructure for future larger clinical trials exploring the use of NAC in patients with CLI and with and without diabetes, and identify a previously unknown novel mechanism of action for NAC.

We believe that previous literature supporting the role of NAC in augmenting compensatory tissue perfusion raises the possibility that this may be an advantageous therapeutic agent to favorably alter the tissue lipidomic profile of diabetic patients receiving NAC. We believe that NAC offers a new treatment strategy for patients with CLI undergoing lower extremity amputation with the intent to improve tissue perfusion, healing, and reduce morbidity and mortality associated with lower limb amputation.

Study Objectives

Primary Aim 1

Determine whether NAC can affect major lower extremity amputation stump perfusion by POD (Post-operative Day) 5

Primary Aim 2

Determine whether NAC can affect major lower extremity stump healing for 30 days following amputation.

Secondary Aim

Determine the effect size in diabetic patients that is necessary to power a larger clinical trial to determine whether NAC treatment can improve tissue perfusion and healing at major lower extremity amputation stumps.

Rationale for the Selection of Outcome Measures

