Upon consent and enrollment in the study, relevant subject information will be relayed to the Barnes Jewish Hospital (BJH) Investigational Pharmacy. Prior to proceeding to the operating room for lower extremity amputation, the patients will be randomized 1:1 by the BJH Investigational Pharmacy to either placebo saline infusion (twice daily) or a standard adult intravenous dose of NAC (1200mg twice daily) for 6 days post-amputation during the usual post-operative inpatient extremity off-loading and stump monitoring period. The pharmacy will maintain blinding, with no member of the investigational team having access to the record until the conclusion of the trial.

Early Withdrawal of Subjects

Patients unable to tolerate the administration of the drug will be withdrawn from the study at any point during their hospitalization and will continue to be monitored until their condition stabilizes. Patients unable to participate in the Post-operative Day 0 Non-invasive Laser Assisted Fluorescence Angiography (LAFA) will be withdrawn from the study at that time point and will not receive the investigational product. Subjects for which continuous IV access is not medically indicated during the 6 day study drug administration period may be withdrawn from the study. Patients unable to participate in follow-up appointments will also be withdrawn from the study.

When and How to Withdraw Subjects

Patients unable to tolerate the administration of the drug will be withdrawn from the study trial at any point during their hospitalization. Patients unable to participate in follow-up appointments will also be withdrawn from the study. They will continue to be monitored for adverse events as inpatients for the duration of their hospitalization. Patients unable to participate in the Post-operative Day 0 Non-invasive Laser Assisted Fluorescence Angiography (LAFA) will be withdrawn from the study at that time point and will not receive the investigational product. No further study follow up will be required.

Data Collection and Follow-up for Withdrawn Subjects

Patient data will be collected up until time of withdrawal from the study and pooled into the collective analysis along with all other patients.

Study Drug

Description

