N-acetyl cysteine (NAC) ((2R)-2-acetamido-3-sulfanylpropanoic acid) is an amino acid derivative of L-cysteine, which is a precursor to glutathione and cysteine. Historically, NAC has been used to treat acetaminophen overdose [6], as well as mucous secretions in patients with cystic fibrosis or chronic obstructive pulmonary disease [24].

Pharmacokinetics including the following [24] :

Distribution: The steady-state volume of distribution (V_{dss}) and the protein binding for acetylcysteine were reported to be 0.47 liter/kg and 83%, respectively.

Metabolism: N-acetyl-cysteine may form cysteine, disulfides, and conjugates in vivo (N, N'-diacetylcysteine, N-acetyl cysteine-cysteine, N-acetyl cysteine-glutathione, N-acetyl cysteine-protein, etc). Based on published data, it was reported that after an oral dose of 35S-acetylcysteine, about 22% of total radioactivity was excreted in urine after 24 hours. No metabolites were identified.

Elimination: After a single intravenous dose of N-acetyl cysteine, the plasma concentration of total N-acetyl cysteine declined in a poly-exponential decay manner with a mean terminal half-life (T_{1/2}) of 5.6 hours. The mean clearance (CL) for N-acetyl cysteine was reported to be 0.11 liter/hr/kg and renal CL constituted about 30% of total CL.

Treatment Regimen

Upon study enrollment, patients will be randomized 1:1 by BJH Investigational Pharmacy to either placebo ½ normal saline infusion (twice a day) or a standard adult intravenous dose of NAC (1200mg twice a day) for 6 days post-amputation. The BJH Investigational Pharmacy will perform this with knowledge of the patient's medical record number (MRN), and without knowledge of any pre-existing medical conditions, comorbidities, past medical history, prior interventions, etc. The first infusion will be administered within three hours from leaving the operating room. The second infusion will be a minimum of 6 hours after the first infusion, or at 21:00 in an attempt to be consistent with routine hospital BID dosing times. Patients will receive their scheduled infusions as long as they are hospitalized according to the chart below (Table 1). **If medication is not administered within that window, dose will not be given to not interfere with the rest of the doses.**

Table 1:

Post-operative Day (POD)	Infusion Schedule
POD 0	1. Within 3 hours from the conclusion of the operation 2. Approximately 6 hours after first infusion, or at 21:00 +/- 6 hours

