Medications will be prepared by the research pharmacy and delivered to the treating nurse; study drug will be blinded to the research team and the study participant. The research pharmacy will

maintain documentation of medication procurement and preparation, as well as randomization, dispensing, and accountability logs. All medications will be stored in a secure location within the research pharmacy and maintained under controlled environmental conditions. Unused doses will be returned to the research pharmacy, whereas used or unwanted partially infused doses will be destroyed on the nursing unit per policy.

Study Procedures

Screening for Eligibility

As discussed in 2.c, subjects that meet study inclusion and exclusion criteria, who are undergoing an elective above-knee or below-knee amputation at the Washington University School of Medicine-affiliated BJH, will be included in this pilot clinical trial.

Potential subjects will be screened by reviewing the weekly operative schedule, and via referral from vascular surgery faculty study co-investigators. Prior to the scheduled operation, eligible patients will be approached for informed consent. Informed consent will be obtained by a member of the vascular surgery research team in accordance with institutional regulations, prior to any further actions in the study. After informed consent is obtained, a baseline clinical evaluation will be performed including lower extremity anthropometric evaluation, medical history and vital signs documentation. Per standard clinical procedures, all patients will also be evaluated by preoperative anesthesia services. Subjects may **participate in the study a second time on ipsilateral or contralateral site if all Inclusion /Exclusion is reviewed and verified prior to second surgery. Patient records from an outside hospital or facility may be obtained and used for screening and/or follow up in patient care.**

Schedule of Measurements

A. Non-invasive Laser Assisted Fluorescence Angiography (LAFA)

Location of Procedure:

- Barnes-Jewish Hospital Operating Rooms
- 4400/8300/7400/7500 Inpatient Hospital Units
- Other Hospital Units also housing vascular surgery patients

Time of Data Collection:

- **Postoperative Day 0:** Obtained in the operating room after amputation, but before placement of dressings.
- **Postoperative Day3:** Obtained following dressing removal at bedside in the inpatient hospital unit.

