 23. Kapp, M.B., *Ethical and legal issues in research involving human subjects: do you want a piece of me?* J Clin Pathol, 2006. **59**(4): p. 335-9.
 24. Holdiness, M.R., *Clinical pharmacokinetics of N-acetylcysteine.* Clin Pharmacokinet, 1991. **20**(2): p. 123-34.

STATISTICAL ANALYSIS PLAN

**Protocol Title: N-Acetyl-Cysteine for Healing of
Amputation Stumps in the Setting of Diabetes**

NCT03253328

**Protocol Version 11.0
Date: March 26, 2020**

Statistical Plan

Sample Size Determination and Power

The purpose of this study is to obtain sufficient preliminary data to determine the sample size necessary for a future large definitive clinical trial. For this pilot study, we plan to enroll 25 patients in each group, allowing for a dropout rate of 10% per group.

We emphasize that effect size (the expected difference in primary outcome between the treatment and control groups) should not be determined by the pilot study. Rather it is determined by the minimum clinically important difference. However, the effect size from the pilot give us some ideas about possible achievable difference.

Interim Monitoring and Early Stopping

An interim analysis will be conducted once >30 patients are enrolled in the study. Analysis will focus on determining differences between NAC and control group. Interim analysis will help determine early differences between the study groups and safety profile of study intervention. The investigators may end the study early depending on study findings, safety profile of the data, and/or if data is adequate for a peer-reviewed publication.

Analysis Plan

Data analysis include (1) the partition of variation of outcome measurements into within and between patient components to obtain standard deviation of measurements, intra-class correlation of the measurements, (2) use of appropriate regression model (GEE or mixed effect regression) to compare the outcome measurements between two groups, while accounting for the intra-class correlation. Interpretation of analysis should be made within the context of a pilot study where we have a pre-specified hypothesis but do not have power analysis for testing the hypothesis.

Statistical Methods

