One of the main study outcomes (and in the future large study) is the stump perfusion assessment, which is a continuous variable measured three times (D0, D3, and D5) after treatment. Based on this longitudinal repeated measurement study design, the preliminary data needed for designing future study include: (1) variance of single measurement, (2) covariance (correlation) among the repeated measurements over time within an individual, (3) level of outcome measurements in patients with and without the treatment.

Missing Outcome Data

Not applicable

Unblinding Procedures

The BJH Investigational Pharmacy will maintain a record of each patient's medical record number and to which arm of the study they were assigned. No member of the vascular surgery investigational team will have access to this information. This will serve to maintain blinding and reduce any unwanted during the trial and subsequent analysis of collected data. Un-blinding of patient data will occur during the interim analysis, and at the end of the study. For un-blinding the pharmacy will then un-blind the study to the investigators such that appropriate conclusions can be made regarding the efficacy of the investigational agent.

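### The Aim 2 healing comparison names no covariate, although a pre-dose stump perfusion reading is a condition of dosing; adjusting for it would probably gain some precision at almost no cost.

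*Combined protocol and SAP*

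**What the plan says.** Primary Aim 2 is to "Determine whether NAC can affect major lower extremity stump healing for 30 days following amputation". For all outcomes, the Analysis Plan (same text in the protocol and the SAP) offers one comparison: "use of appropriate regression model (GEE or mixed effect regression) to compare the outcome measurements between two groups", with allowance for intra-class correlation. It names no covariate and excludes none.

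Four other places bear on the point:

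- **Timing of the reading.** Under Schedule of Measurements, the POD 0 LAFA is "Obtained in the operating room after amputation, but before placement of dressings".
- **Timing of the drug.** Under Treatment Regimen, "The first infusion will be administered within three hours from leaving the operating room". The reading is therefore pre-dose.
- **Completeness.** Under Early Withdrawal of Subjects, a patient unable to have that LAFA "will be withdrawn from the study at that time point and will not receive the investigational product".
- **Link to healing.** The Background states that "healing at the surgical site in patients with diabetes is impaired due to poor blood flow at the arterial cul-de-sac".

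The SAP's Statistical Methods nevertheless describe perfusion as a "continuous variable measured three times (D0, D3, and D5) after treatment", which counts D0 as an outcome. The one statement that relates other data to a healing score, in the Data Analysis note under Anthropometric Measurements, concerns the anthropometric data. No stratification is described, and the pharmacy randomizes without clinical information.

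**The concern.** Healing has no baseline of its own, because the wound is created at the operation. The nearest thing to a baseline is the perfusion of the new stump before any drug is given. The trial collects that reading as a condition of dosing, and its own rationale ties it to healing.

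If the reading does predict healing, a two-group comparison leaves the variation it explains in the error term. At about 22 patients per arm, that widens the interval around the healing difference. This matters for a pilot whose stated purpose is to supply planning figures for a larger trial. The residual variance of healing after adjustment, and the strength of the link between baseline perfusion and healing, are themselves useful planning quantities. The list in Statistical Methods is framed around the perfusion series and covers neither.

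**Working it through.** **Plan's own figure.** There is no power calculation to reproduce. Only the dropout step can be checked: 25 × 0.9 = 22.5 evaluable per arm, and 22 / 0.9 = 24.4, which rounds up to 25. I use 22 per arm, N = 44.

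**Is the reading a legitimate covariate?** Randomization comes before surgery, so POD 0 LAFA is obtained after randomization. But no drug has been given and allocation is blinded, so treatment cannot have affected the reading. The same is not true of D3 and D5. A patient withdrawn for lack of the reading needs no further study follow-up, so adjustment should not remove anyone who contributes a healing outcome.

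**Assumptions.** Healing is a continuous score. Its correlation r with POD 0 LAFA is not in the documents, so I take 0 to 0.7.

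**Where the loss comes from.** In SD units, the unadjusted difference has variance 2/22 = 0.0909. The chance difference between arms in baseline perfusion has the same variance, with SD √(2/22) = 0.302. It enters the healing difference multiplied by r, so it contributes r² × 2/22. Chance imbalance is thus a fraction r² of the variance already in the unadjusted standard error.

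**Net effect of adjusting.** Estimating the slope has a cost, so the variance ratio, adjusted to unadjusted, is (1 − r²)(N − 3)/(N − 4). Here (N − 3)/(N − 4) = 41/40 = 1.025.

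| r | 1 − r² | variance ratio | equivalent total, 44 / ratio |
|---|---|---|---|
| 0 | 1.00 | 1.025 | 42.9 |
| 0.1 | 0.99 | 1.015 | 43.4 |
| 0.2 | 0.96 | 0.984 | 44.7 |
| 0.3 | 0.91 | 0.933 | 47.2 |
| 0.5 | 0.75 | 0.769 | 57.2 |
| 0.7 | 0.51 | 0.523 | 84.2 |

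Break-even is where 1 − r² = 40/41, so r = √(1/41) = 0.156.

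**In terms of detectable effect.** With two-sided alpha 0.05 and 80% power (both assumed), the unadjusted figure is (1.960 + 0.842) × 0.302, or 0.84 SD. Multiplying by the square root of the ratio gives 0.82 at r = 0.3 and 0.74 at r = 0.5.

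**If all 25 per arm are analysed.** The factor becomes 47/46 = 1.022. The ratios are 0.93 at r = 0.3 and 0.77 at r = 0.5, with break-even at 0.15.

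**If healing is binary.** I simulated 4,000 trials of 25 per arm with failure of 40% against 20%. The 40% is the re-amputation or revision figure in the Study Abstract; the 20% is assumed. The variance ratio for the risk difference, from linear adjustment, was 1.01, 0.98 and 0.86 for a log odds ratio per SD of baseline perfusion of 0, 0.5 and 1.0.

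**The case against.** The strongest reply is that the plan is silent, not wrong. It promises an appropriate regression model and rules nothing out. A reader might infer that the SAP has decided against adjustment; the text does not say so. What stands is that no covariate is committed to, and that the investigators are unblinded at the interim analysis. A covariate chosen after that point is less credible than one named now.

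A reader might also infer that chance imbalance in starting perfusion biases the healing result, or is a second harm on top of lost precision. Neither follows. The unadjusted estimate is unbiased over randomizations, its type I error is preserved, and the imbalance is what the r² term already counts.

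Three further objections have force:

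- **The correlation is assumed.** The Background statement is about mechanism, in diabetic patients. It does not show that one operating-room reading predicts healing weeks later in a population with and without diabetes. If r is about 0.2 or less, adjustment changes little.
- **Healing is not defined.** The documents give no scale, model or single time point for the healing score. LAFA quantitative peak perfusion is named but its derivation is not described. A covariate has to attach to a defined outcome.
- **Power is not the pilot's criterion.** The plan says so itself. The benefit should therefore be read as a narrower interval and better planning figures.

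Other pre-dose characteristics, such as amputation level and diabetes status, are also available. The case for POD 0 LAFA is that the protocol links it to healing and makes it a condition of dosing; the documents do not show it to be the best predictor.

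Finally, the LAFA section says that a contraindication to LAFA does not exclude a patient from other measurements, which sits awkwardly with the withdrawal rule. The remark is attached to dye allergy, itself an exclusion criterion, so it probably affects few patients, but the two passages must be reconciled.

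**Conclusion.** The point holds as an inexpensive improvement in precision. The only stated healing comparison names no covariate, while a pre-dose reading that the protocol links to healing is required before dosing.

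For a continuous score with 22 per arm, the net variance reduction is about 7% at r = 0.3 and 23% at r = 0.5. Using 1 − r² alone would suggest 9% and 25%, but that omits the cost of estimating the slope. Below r of about 0.16 there is a small net loss, reaching 2-3% of variance at r = 0. A binary outcome would gain less.

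The facts about timing and the missing covariate come directly from the documents. The size rests entirely on an assumed r and on a healing score that is not yet defined. Nothing here supports a claim that the planned comparison is biased or invalid.

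**What to change.** In the SAP Analysis Plan, state that the primary Aim 2 comparison, on the healing score at the post-discharge visit (Visit 1), is adjusted for the POD 0 LAFA quantitative peak perfusion value. Enter it as one continuous, pre-specified covariate, and show the unadjusted result beside it. Add a short definition of the healing score and of how the perfusion value is derived, since the covariate has no meaning without them. D3 and D5 perfusion should not be used as covariates, because they follow dosing.

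In Statistical Methods, describe D0 as a pre-dose baseline rather than as a post-treatment measurement. Reconcile the LAFA contraindication note with the withdrawal rule.

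The cost is a few lines of SAP text and one degree of freedom, with no new data. The downside is a slight loss of precision if the correlation proves to be near zero.

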POD 1	1. 9:00 +/- 6 hours 2. 21:00 +/- 6 hours
POD 2	1. 9:00 +/- 6 hours 2. 21:00 +/- 6 hours
POD 3	1. 9:00 +/- 6 hours 2. 21:00 +/- 6 hours
POD 4	1. 9:00 +/- 6 hours

	2. 21:00 +/- 6 hours
POD 5	1. 9:00 +/- 6 hours 2. Anticipated discharge, second infusion may be given if patient is still inpatient or missed any doses

Preparation and Administration of Study Drug

All investigational doses will be prepared by the research pharmacy and prepared in a manner that both active and placebo doses appear identical to protect the blind. Preparation of each dose will be performed using aseptic technique, and within a laminar flow hood. Each dose will be a total volume of 50 mL and will be administered over a period of 30 minutes through an IV. N-acetyl-cysteine will not be infused in the same intravenous line as iron-products, cefepime, or ceftazidime.

Subject Compliance Monitoring

The Barnes-Jewish Hospital inpatient electronic medication administration record (eMAR) will be used to assess compliance; significant patient noncompliance, defined as refusal or inability to adhere to the protocol requirements, will lead to subject withdrawal.

Prior and Concomitant Therapy

Use of any investigational agent within 30 days before the first dose of study drug and until after the last evaluation will not be allowed. Since concomitant use of N-acetyl-cysteine and carbamazepine may cause decrease carbamazepine plasma concentrations resulting in an increased risk of seizures, patients who are receiving carbamazepine will not be enrolled in the study.

Concurrent use of N-acetyl-cysteine and nitroglycerin may result in enhanced hypotension and nitroglycerin-induced headache. Therefore patients who receive both agents will be monitored by members of the study team for any potential anticipated complications.

All other concomitant medications that are necessary for the health and well-being of the patient that are not specifically prohibited by the protocol are permitted.

Packaging

Acetadote (acetyl-cysteine) Injection is available as a 20% solution (200mg/mL) in 30 mL single dose glass vials. Acetadote is sterile and can be used for I.V. administration.

Blinding of Study Drug

All intravenous doses will be prepared in identical evacuated IV containers with a total volume of 50mL. N-acetyl cysteine is a clear and colorless solution, and no additional blinding material will be required.

Receiving, Storage, Dispensing and Return

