2. Clean the selected measuring site with alcohol or other skin-preparation solution.
3. Dry the site well with a gauze pad.
4. Take a standard fixation ring.

5. Remove the fixation ring from the protective film.

6. Apply the fixation ring to the measuring site as follows:
 - Press the center of the fixation ring onto the measuring site with a finger.
 - Run a finger around the rim circumference.

Note: Press firmly to prevent leaks.

7. Fill the hole in the fixation ring with 3-5 drops of the contact liquid.

8. Affix the electrode into the fixation ring as follows:
 - Align the arrow on the electrode with one of the marks on the fixation ring.
 - Turn the electrode 90° clockwise to fasten it in the fixation ring.

9. Repeat steps 1 to 8 if more electrodes are to be applied.

Wait for a stable reading after the electrode has been affixed to the patient.

Note: The physiological stabilization time of a patient is 15-20 minutes for the tcpO₂ reading. During this time the electrode will slowly heat the skin, making the arteries dilate. Longer time may indicate an incorrect attachment of the electrode or a poorly selected measuring site.

C. Anthropometric Measurements

Location of Procedure:

- Barnes-Jewish Hospital Operating Rooms
- Inpatient Hospital Units
- Other Hospital Units also housing vascular surgery patients

Measurements:

Measurements will be collected as long as the patient is hospitalized, including:

1. Temperature (daily maximum and minimum)
2. Blood Pressure Range

3. Heart Rate Range
4. SpO₂ Range
5. Respiratory Rate Range
6. Amputation wound assessment on POD 3 (if stump dressings are off and still hospitalized) and POD 5 (if stump dressings are off and still hospitalized).

In addition, a blood sample (~50mL; 3-4 table spoons) may be obtained for:

1. Hospital laboratory evaluations that may be obtained per standard of care, at standard of care time points during the hospital stay

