2. The patient is scanned under an existing non-contrast MRI protocol to obtain blood flow and tissue oxygenation pictures at rest.

3. Each study patient is carefully monitored by a physician, nurse practitioner, physician assistant or nurse for signs and symptoms of allergic reaction or intolerance to this non-invasive procedure until discharge.

Visit 1

Following patient discharge, amputation stumps will be evaluated within 20-50 days during a routine post-operative visit using the same anthropometric parameters (LAFA and TcPO₂ will not be performed at this time point).

Safety and Adverse Events

Safety and Compliance Monitoring

All study patients are inpatients at BJH in St. Louis Missouri and are cared for by appropriately trained nurses on the inpatient wards. Vascular surgery Attending Physicians, Vascular Surgery Fellows, Surgical Residents, and a team of Nurse Practitioners oversee their overall care. Inpatient ward nurses routinely assess patients at least every 4 hours with vital signs, intake and output measurements, pain assessment, nutrition assessments, medication review and administration, etc.

Medical Monitoring

Medical monitoring of the study will be performed by the Principal Investigator. The goal of monitoring this study is to enhance human subject protection and to monitor the quality of the clinical trial data by focusing investigator oversight on the most important aspects of study conduct and reporting. The PI will provide regular oversight to ensure adequate protection of the rights, welfare, and safety of the human subjects and the quality of the clinical trial data.

Definitions of Adverse Events

An adverse event (AE) is defined as any untoward medical occurrence in a subject administered a pharmaceutical product or who has undergone study procedures and which does not necessarily have a causal relationship with this treatment. An AE can therefore be any unintended sign (including an abnormal laboratory finding), symptom, or disease temporally associated with the use of the investigational product, whether or not related to the medicinal (investigational) product.

All AEs will be recorded in the CRF from the time of consent through the 30 days post-operative visit. AEs will be followed to resolution or stabilization.

An abnormality identified during a medical test (e.g., laboratory parameter, vital sign, physical exam) should be defined as an AE only if the abnormality meets one of the following criteria:

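### A randomised patient with no medical need for continuous IV access may be withdrawn from the whole study rather than from study drug, which gives up healing data that need no line

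*Combined protocol and SAP*

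**What the plan says.** Patients are randomised before they go to the operating room (Randomization Method and Blinding). Early Withdrawal of Subjects then adds a ground that acts after randomisation: "Subjects for which continuous IV access is not medically indicated during the 6 day study drug administration period may be withdrawn from the study". The companion section, When and How to Withdraw Subjects, does not mention this ground.

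Data Collection and Follow-up for Withdrawn Subjects sets the consequence for every withdrawn patient: "Patient data will be collected up until time of withdrawal from the study and pooled into the collective analysis along with all other patients". The documents describe no status in which a patient stops study drug and stays in follow-up.

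An incomplete course of drug is otherwise tolerated. On a missed dosing window, Treatment Regimen says: "If medication is not administered within that window, dose will not be given to not interfere with the rest of the doses". Infusions run only while the patient is in hospital, and the POD 5 row of Table 1 reads: "Anticipated discharge, second infusion may be given if patient is still inpatient or missed any doses".

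Healing over 30 days is Primary Aim 2. After discharge, "amputation stumps will be evaluated within 20-50 days during a routine post-operative visit" (Visit 1), with neither LAFA nor TcPO2 at that visit.

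**The concern.** The reason for this withdrawal is how the drug is delivered, but the permitted consequence is leaving the trial. Visit 1 is the only healing assessment scheduled after discharge, and it takes place at a routine visit. A patient withdrawn on this ground has no Visit 1 outcome in the trial, even if the surgical team sees the stump on the normal date.

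The planned GEE or mixed model can use readings taken before withdrawal. It cannot supply a late healing outcome that was never recorded, and the Missing Outcome Data section is marked as not applicable, so nothing offsets the loss. What is at stake is the discretionary and avoidable loss of a primary outcome in randomised patients, in a pilot meant to inform a larger trial.

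**Working it through.** **1. Which assessments need a line**

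| Assessment | Schedule | IV line needed? |
|---|---|---|
| LAFA | POD 0, 3, 5 | Yes: ICG is injected intravenously |
| TcPO2 | Day 0, POD 3, POD 5, when possible | No: skin electrodes |
| Wound assessment | POD 3, POD 5, if dressings are off and patient is in hospital | No |
| Visit 1 | 20-50 days, after discharge | No |

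Three of the four can continue without a line. Perfusion readings taken before withdrawal are kept in the analysis, so the avoidable loss falls mainly on healing.

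**2. The plan's own figure.** 25 per arm with 10% dropout gives 25 × 0.90 = 22.5 per arm, or 45 in total. No power, effect size or SD is stated, so the sample size cannot be reproduced further. The 10% is not broken down by reason. If it already covers this ground, 45 remain and there is no added loss.

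**3. Precision, illustration only.** The documents give no rate, so assume 5, 10 or 15 patients are lost beyond the allowance. For a continuous outcome measured once per patient, with n patients in two equal arms, the 95% half-width for the arm difference is 1.96 × √(4/n) in SD units.

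| n | Half-width (SD) |
|---|---|
| 45 | 0.584 |
| 40 | 0.620 |
| 35 | 0.663 |
| 30 | 0.716 |

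No healing scale is defined, so the result stays in SD units. It does not apply to perfusion.

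**4. Dilution if these patients are kept.** Table 1 schedules 2 infusions on POD 0, 8 on POD 1-4 and 1 or 2 on POD 5, which makes 11 or 12. Assume the effect is proportional to the number of infusions. With k patients of 45 stopping early, dilution = (k/45) × (1 − given/scheduled).

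| Stop after | Given | Shortfall (of 11 / of 12) | k = 5 | k = 15 |
|---|---|---|---|---|
| POD 1 | 4 | 0.636 / 0.667 | 7.1-7.4% | 21.2-22.2% |
| POD 2 | 6 | 0.455 / 0.500 | 5.1-5.6% | 15.2-16.7% |
| POD 3 | 8 | 0.273 / 0.333 | 3.0-3.7% | 9.1-11.1% |

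A stop before the end of POD 1 would dilute more.

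**5. Balance of the two.** Compare effect relative to half-width for k = 5. Withdrawing them gives 1/0.620 = 1.61. Keeping them gives about 0.93/0.584 = 1.59 (stop after POD 1), 0.944/0.584 to 0.949/0.584 = 1.62 (POD 2), or 0.963/0.584 to 0.970/0.584 = 1.65-1.66 (POD 3). Keeping them is slightly worse, about equal or slightly better, depending on when they stop. Power does not decide the matter.

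**The case against.** The strongest reply is that no harm is demonstrated. The rule is permissive, so the team can already keep a patient in. The group is narrow: discharge does not trigger this rule, because infusions simply end at discharge. What remains is inpatients in the dosing period without a clinical need for a line whom the team chooses to withdraw. That may be several patients or none. This stands, and it limits the priority.

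A second reply is that other grounds are more forceful. Drug intolerance leads to mandatory withdrawal and also ends Visit 1 data. This stands too: the rule on IV access is one instance of stopping drug being treated as leaving the study. It does not make this instance sound.

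A third is that this is a pilot without a power analysis, that the design data it lists concern perfusion, and that Visit 1 may fall beyond 30 days. All of that is true, but healing is still a primary aim and Visit 1 is its only scheduled assessment after discharge.

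A reader might also infer that Subject Compliance Monitoring forces these patients out, since "significant patient noncompliance, defined as refusal or inability to adhere to the protocol requirements, will lead to subject withdrawal". That reading is strained. A clinical judgement that a line is not indicated is not naturally patient noncompliance, and a mandatory reading would leave the permissive rule with no purpose. Nor is the rule without a criterion: it states one, and lacks only guidance on using the discretion.

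**Conclusion.** The point holds in a limited form. The protocol permits whole-study withdrawal of a randomised patient for a drug-delivery reason and then ends data collection. Visit 1 healing, POD 3 and POD 5 wound assessment, and TcPO2 where available can be lost although none of them needs a line. I found no text that restores them: the provision for continued adverse event monitoring covers the hospital stay only.

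The size is unknown. It may be zero beyond the 10% allowance, and the half-widths above rest on assumed losses. A reader might infer that the rule biases the arm comparison. The documents do not support that. They show neither bias nor a direction, and identical-looking infusions on one schedule in both arms give no ground for assuming unequal loss. A gain in power should not be claimed either, since dilution under the proportional-dose assumption can cancel the gain in precision. The argument is for complete healing data analysed as randomised. Priority is low to moderate: a change worth considering.

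**What to change.** In Early Withdrawal of Subjects, for this ground only, replace withdrawal from the study with: *may discontinue study drug but will remain in the study*. State that these patients keep the POD 3 and POD 5 wound assessments, TcPO2 when available and Visit 1; that LAFA is done only if access for the ICG injection exists; that the date and reason for stopping are logged; and that they are analysed in the arm to which they were randomised. No line is then kept in only for research.

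Optionally, add a line to Subject Compliance Monitoring that infusions missed on this ground are not noncompliance.

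The cost is a change of wording and one log entry. The assessments are already scheduled and Visit 1 is a routine visit. The downside is the dilution shown above. POD 3 and POD 5 LAFA may still be lost, so the change does not recover all perfusion data.
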